Treatment period	The time period from administration of the first dose of study drug through the end of the one month post-treatment discontinuation visit.

[figure not shown]

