
(3) Sequential administration of chemotherapy followed by a TKI is feasible and can achieve synergistic cytotoxicity.

Study Design

Open label, dose de-escalation, phase 1b pilot trial of crenolanib with standard salvage chemotherapy. Subjects may receive up to 2 cycles of induction with standard salvage chemotherapy followed by crenolanib. Each arm will enroll approximately 24 patients (72 total); stratification to each arm will be per physician's choice.

Arm A (HAM + crenolanib)

Subjects 18-60 years of age who have not undergone a prior allogeneic hematopoietic stem cell transplant (HSCT):

- Mitoxantrone 10 mg/m² IV, over ≤ 30 mins days 1-3
- Cytarabine 1000 mg/m² IV, over 3 hours days 1-6
- Crenolanib 100 mg TID p.o. starting day 7 (+3 day)

For subjects > 60 years, or subjects who have undergone a prior allogeneic HSCT, or subjects who need a second re-induction HAM cycle, the following reduced doses will be used:

- Mitoxantrone 8 mg/m² IV, over ≤ 30 mins days 1-3
- Cytarabine 500 mg/m² IV, over 3 hours days 1-6
- Crenolanib 100 mg TID p.o. starting day 7 (+3 day)

Arm B (MEC + crenolanib)

Patients >18 years of age:

- Mitoxantrone 8 mg/m² IV, push days 1-5
- Etoposide 100 mg/m² IV days 1-5
- Cytarabine 1000 mg/m² IV, over 3 hours days 1-5
- Crenolanib 100 mg TID starting day 7 (+3 day)

Arm C (FLAG-Ida + crenolanib):

Patients >18 years of age:

- Fludarabine 30 mg/m² IV day 1-5
- Cytarabine 2 g/m² IV over 2 hrs day 1-5
- G-CSF 300 ug s.c. inj or IV/5ug/kg SC day 6 - neutrophil recovery
- Idarubicin 8 mg/m² IV over 30 min day 1-3
- Crenolanib 100 mg TID starting day 7 (+3 day)

Primary Objective

- To determine the safety, dose limiting toxicities and maximum tolerated dose (or confirm the target dose of 100 mg TID) of crenolanib given sequentially following standard salvage chemotherapy regimens in subjects with refractory/relapsed AML

Secondary Objectives

- To determine the response rate, duration of response, progression-free survival, and overall survival of crenolanib when given sequentially following standard salvage chemotherapy regimens in subjects with refractory/relapsed AML
- To determine the pharmacokinetics of crenolanib when given sequentially following standard salvage chemotherapy regimens in subjects with refractory/relapsed AML

Inclusion Criteria

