1. Confirmed diagnosis of AML, including treatment-related secondary AML (except prior MDS) according to World Health Organization (WHO) 2008 classification at treating institution
2. Subjects who are refractory* or who have relapsed** following first line AML therapy with cytarabine/anthracycline based chemotherapy, with or without a tyrosine kinase inhibitor.

*Refractory to induction therapy is defined as never achieving CR, CRi or CRp (according to International Working Group criteria) after one line of intensive regimen for AML (re-induction, consolidation and/or transplant allowed) including at least one cytarabine containing induction block with a total dose no less than 700mg/m² per cycle and 3 days of an anthracycline with or without a TKI.

or

**First relapse is defined as untreated hematologic relapse (according to International Working Group criteria) after one line of intensive regimen for AML (re-induction, consolidation and/or transplant allowed) including at least one cytarabine containing induction block with a total dose no less than 700mg/m² per cycle and 3 days of an anthracycline with or without a TKI that induced a CR/CRi/CRp. Subjects are allowed to receive induction, consolidation, transplant and/or maintenance prior to achieving their first CR/CRi/CRp.

3. Subjects considered eligible for intensive chemotherapy
4. ECOG performance status ≤ 2
5. Age ≥ 18 years
6. Adequate liver function within 72 hours of enrollment, defined as:
 - Normal total serum bilirubin
 - ALT and AST $\leq 2.0 \times$ ULN
7. Adequate renal function, defined as serum creatinine $\leq 1.5 \times$ ULN
8. Women of childbearing potential must have a negative serum or urine pregnancy test with a sensitivity of at least 25 mIU/mL within 72 hours prior to enrollment

“Woman of childbearing potential” is defined as any woman who has not undergone a hysterectomy and who has had menses at any time in the preceding 24 consecutive months

9. Women of child-bearing potential must either commit to continued abstinence from heterosexual intercourse or begin one acceptable method of birth control (IUD, tubal ligation, or partner’s vasectomy) while on crenolanib and for 3 months following the last dose of crenolanib.

Hormonal contraception alone is not an acceptable method of birth control for the purpose of this trial.

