13. Subject with uncontrolled cardiac disease including congestive heart failure class III or IV by the NYHA, unstable angina (anginal symptoms at rest) or new onset angina (began within the last 3 months) or myocardial infarction within the past 6 months
14. Subject with concurrent severe and/or uncontrolled medical or psychiatric conditions that in the opinion of the investigator may impair the participation in the study or the evaluation of safety and/or efficacy
15. Inability to give an informed consent

Statistical Methods

Initially, the study will evaluate DLT and determine the maximum tolerated dose (or confirm the target dose of 100 mg TID) of crenolanib in combination with either HAM (Arm A), MEC (Arm B) or FLAG-Ida (Arm C) chemotherapy. Thereafter, the study will include a dose-expansion cohort.

For each arm, an initial 6 subjects will be enrolled at a crenolanib dose of 100 mg TID and will be evaluated for DLT, as follows:

- The DLT period will be 28 days
 - Assessment of potential hematologic DLTs that started during the DLT period will extend for up to 6 weeks following the start of the event (see definition of hematologic DLT)
- DLT will be defined as any clinically significant adverse event or abnormal laboratory value that

is not related to concomitant medications, co-morbidities or underlying disease (leukemia), and that is not expected for the chemotherapy being used together with crenolanib

The following will be considered to be DLT:

Non-hematologic DLT:

- Any grade 3 or 4 non-hematologic toxicity despite optimal supportive care
 - For example, grade 3 or 4 nausea, vomiting, or diarrhea that cannot be controlled with standard antiemetic or antidiarrheal medications used at optimal dose within 72 hours of onset
- Any tumor lysis syndrome

Hematologic DLT:

- Grade ≥ 3 neutropenia and/or thrombocytopenia with a hypocellular bone marrow lasting for 6 weeks or more after the last dose of therapy in the absence of residual leukemia (i.e., with less than 5% blasts)
 - Anemia will not be considered a DLT

For each arm, prior to determining the maximum tolerated dose (or confirming the target dose of 100 mg TID) of crenolanib based on DLT, subjects will be enrolled in a sequential manner such that no more than 6 subjects are within 30 days of starting induction 1 therapy. See Section 12.2.1 for dose de-escalation and stopping rules based on dose-limiting toxicity.

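### Extended follow-up for the hematologic DLT runs 6 weeks from event start and only for events starting in the DLT period, but the definition runs 6 weeks from the last dose, so qualifying cases can be missed

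*Combined protocol and SAP*

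**What the plan says.** The relevant rules are in the Synopsis (Section 1).

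- **DLT period** (Statistical Methods): "The DLT period will be 28 days". No start day is given there.
- **Extended assessment** (Statistical Methods): "Assessment of potential hematologic DLTs that started during the DLT period will extend for up to 6 weeks following the start of the event". This bullet then refers the reader to the hematologic DLT definition.
- **Hematologic DLT** (Statistical Methods): Grade 3 or higher "neutropenia and/or thrombocytopenia with a hypocellular bone marrow lasting for 6 weeks or more after the last dose of therapy", with marrow blasts below 5%. Anemia does not count.
- **Attribution** (Statistical Methods): an event is not a DLT if it is due to the leukemia, other illness or other medication, or is expected from the chemotherapy backbone.
- **Entry** (Inclusion and Exclusion Criteria): there are liver and renal limits, but none of the 13 inclusion and 15 exclusion criteria sets a neutrophil or platelet minimum. Inclusion 13 requires clinically significant toxicity of prior therapy to have resolved to Grade 1 or lower. Exclusion 1 requires at least 5% blasts unless there is measurable extramedullary disease.
- **Timing** (Study Design): chemotherapy begins on day 1 and crenolanib on day 7, with a 3-day allowance. Cytarabine ends on day 6 in Arm A and day 5 in Arms B and C.

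**The concern.** Prolonged marrow aplasia is the only hematologic toxicity that can count as a DLT, and a 28-day period is too short to show it. Detection therefore depends on the extension, which differs from the definition in two ways.

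First, the extension counts 6 weeks from the start of the event, while the definition counts them from the last dose. A cytopenia that starts before the last dose is followed for too short a time. Second, the extension covers only events that start inside the DLT period. A subject with active leukemia may enter already at Grade 3 or worse, clear the leukemia and remain aplastic. That subject can meet the definition, but on a literal reading no extended assessment is called for.

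The primary objective is to find the maximum tolerated dose or confirm the target dose, starting with six subjects per arm. In a cohort of six, one missed event matters, and the error runs in one direction only.

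**Working it through.** The plan states no figure to reproduce here, so the check is day arithmetic followed by an illustration. Day 1 is the first day of chemotherapy.

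**Inputs** (all from the Synopsis): a 28-day period; a 6-week (42-day) extension from event start; a 42-day duration from last dose; last cytarabine on day 5 or 6; first crenolanib on days 7 to 10; six subjects in the initial cohort of each arm. The text does not say whether the last dose of therapy means chemotherapy or crenolanib, so both are tried.

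**Step 1: when the period closes.** With start day S, it closes on day S + 27.
- S = 1: days 1–28
- S = 7: days 7–34
- S = 10: days 10–37

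**Step 2: when the duration is first met.** With last dose on day L, this is day L + 42.
- L = 5: day 47
- L = 6: day 48
- L = 7 (a single day of crenolanib): day 49

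The latest close is day 37 and the earliest qualifying day is 47. The definition cannot be met inside the period under any start day, and the extension is always needed.

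**Step 3: the two clocks.** With onset on day O, follow-up ends on day O + 42 and the definition needs day L + 42. The shortfall is (L + 42) − (O + 42) = L − O, which is positive whenever onset precedes the last dose.

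| Onset O | Last dose L | Followed to | Needed | Shortfall |
|---|---|---|---|---|
| 3 | 6 | 45 | 48 | 3 days |
| 3 | 7 | 45 | 49 | 4 days |
| 10 | 28 | 52 | 70 | 18 days |
| 14 | 6 | 56 | 48 | none |

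The value L = 28 is an assumption; the available text does not say how long crenolanib continues.

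**Step 4: the onset condition.** Events with O < S get no extension.
- S = 1: only cytopenia present before chemotherapy is left out.
- S = 7: onset on days 1–6 is also left out.
- S = 10: onset on days 1–9 is also left out.

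**Step 5: illustration of the consequence.** Let p be the true rate of qualifying prolonged cytopenia and q the share of such cases that the rule misses. Both are assumptions; the documents give neither. Put r = p(1 − q), treat subjects as independent and ignore non-hematologic DLTs. Then P(at least 1 of 6) = 1 − (1 − r)^6, and P(at least 2 of 6) = 1 − (1 − r)^6 − 6r(1 − r)^5. Each cell gives these two probabilities in that order.

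| p | q = 0 | q = 0.25 | q = 0.50 | q = 0.75 |
|---|---|---|---|---|
| 0.20 | 0.738 / 0.345 | 0.623 / 0.224 | 0.469 / 0.114 | 0.265 / 0.033 |
| 0.33 | 0.910 / 0.642 | 0.818 / 0.460 | 0.661 / 0.259 | 0.403 / 0.082 |
| 0.50 | 0.984 / 0.891 | 0.940 / 0.726 | 0.822 / 0.466 | 0.551 / 0.167 |

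At q = 1 every entry is 0. The cut-offs of one and two events are illustrations, because the trial's own threshold is in Section 12.2.1, which was not in the text available to me.

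**The case against.** **The event is a composite.** A potential hematologic DLT needs low counts, a hypocellular marrow and no residual leukemia together. Most subjects who are cytopenic at entry have at least 5% blasts, so the event may be said to start only when the marrow empties after chemotherapy. This is a natural reading and would bring many baseline-cytopenic subjects back under the rule. The text does not say that this is what the start of the event means. Nor does this reading remove the clock conflict: a marrow that empties on day 10, with crenolanib last given on day 28, is followed to day 52 but needs day 70. If the last dose means chemotherapy and the marrow empties afterwards, there is no shortfall.

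**The definition has no onset condition, and the follow-up bullet refers to it.** This stands. A reader might infer that early-onset cytopenia can never become a DLT. The documents do not support that: a site could still report such a case, and a subject neutropenic at entry could qualify through new thrombocytopenia. What is missing is planned follow-up to detect it.

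**The DLT period may start on induction day 1.** This also stands. The staggering rule in the same part of the Synopsis counts from the start of induction 1. The Treatment period definition, "The time period from administration of the first dose of study drug through the end of the one month post-treatment discontinuation visit", counts from study drug, but it defines a different term. Cytopenia that starts during chemotherapy falls outside the period only if the period opens at crenolanib.

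**Some of the exclusion is deliberate.** The attribution rule removes events due to leukemia or expected from chemotherapy, and inclusion 13 limits prior-therapy toxicity at entry. But inclusion 13 does not reach cytopenia caused by leukemia. The requirements for low blasts and 6 weeks' duration already address disease attribution more directly than an onset date does.

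**Section 12.2.1 may settle some of this.** It may define the start day or evaluability, so the point is limited to the Synopsis wording.

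**Conclusion.** The Synopsis is internally inconsistent, and the two passages must be reconciled. The extension is the only route to the hematologic DLT, yet its follow-up ends L − O days too early whenever the event begins before the last dose. Read literally, it also gives no extended assessment for cytopenia present before the period opens. The shortfall in follow-up does not depend on which day starts the period. The omission of pre-existing cytopenia depends on what counts as the start of the event. Omission of cytopenia starting during chemotherapy depends on a start day that the available text does not give.

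The size is unknown. A reader might infer that many subjects are affected, or that the target dose is demonstrably easier to confirm. The documents give no frequency of baseline cytopenia, no onset timing, no rate of prolonged aplasia and, in the text available, no decision threshold, so neither inference is supported. The table in the working shows only how the result moves with the assumed p and q. The direction is clear: missed events can only lower the DLT count.

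**What to change.** - Reconcile the follow-up bullet with the definition, so that hematologic follow-up runs to the same point, 6 weeks from the last dose of therapy, for every DLT-evaluable subject whatever the onset date. Say which drug's last dose is meant.
- Keep the attribution rule for leukemia and chemotherapy, and state how it applies to cytopenia already present at baseline.
- State which day starts the 28-day period.
- Check all of this against Section 12.2.1.

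**Cost.** The change is mainly wording. Some subjects would need counts and a marrow later than the present bullet requires, so a cohort's hematologic assessment may close later. The assessment schedule was not in the text available, so whether those samples are already planned should be checked. Slow recovery that is partly due to prior therapy may be counted, so the DLT rate may look slightly less favourable.

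### The synopsis frees an enrolment slot 30 days after induction starts, before any hematologic DLT can be established (day 43 at the earliest, day 70 or later for a late event)

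*Combined protocol and SAP*

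**What the plan says.** All of this is in the Synopsis, mainly under Statistical Methods.

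- First cohort: "For each arm, an initial 6 subjects will be enrolled at a crenolanib dose of 100 mg TID and will be evaluated for DLT".
- Spacing: the limit applies "prior to determining the maximum tolerated dose (or confirming the target dose of 100 mg TID) of crenolanib based on DLT", and it is that "no more than 6 subjects are within 30 days of starting induction 1 therapy".
- Window: "The DLT period will be 28 days". The text reviewed does not give its first day.
- Extension: "Assessment of potential hematologic DLTs that started during the DLT period will extend for up to 6 weeks following the start of the event".
- Hematologic criterion: grade 3 or worse neutropenia or thrombocytopenia "with a hypocellular bone marrow lasting for 6 weeks or more after the last dose of therapy in the absence of residual leukemia".

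The reader is then referred to Section 12.2.1 for the de-escalation and stopping rules. That section was not in the text available for this review. The dose question is the primary objective: "To determine the safety, dose limiting toxicities and maximum tolerated dose (or confirm the target dose of 100 mg TID) of crenolanib".

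**The concern.** Sequential enrolment before dose determination is meant to let the toxicity of the first subjects inform the exposure of the next. The plan recognises that marrow toxicity takes longer to judge than other toxicity and extends its assessment accordingly. The spacing limit was not extended with it. A subject drops out of the count after 30 days whether or not the hematologic assessment is still open. An arm that never starts more than six subjects in 30 days is not paused by the limit at all.

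If prolonged aplasia then emerges in the first six, any de-escalation follows further exposure at the same dose. Fewer of the roughly 24 subjects in that arm remain to characterise the dose finally chosen.

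**Working it through.** The plan states no figure to reproduce here. The check is calendar arithmetic, with the start of induction 1 as day 1.

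**Inputs** (Synopsis, Study Design and Statistical Methods)
- Last chemotherapy: day 6 in Arm A; day 5 in Arms B and C (G-CSF not counted).
- Crenolanib starts on day 7 to 10; no last day is given in the text reviewed.
- DLT period: 28 days. Each 6-week clock: 42 days.
- Limit: six subjects within 30 days of starting. Arm size: about 24.

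**When a hematologic DLT can be established**

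| Reading | Sum | Day |
|---|---|---|
| Event-start clock, onset day 1 | 1 + 42 | 43 |
| Last chemotherapy, Arms B and C | 5 + 42 | 47 |
| Last chemotherapy, Arm A | 6 + 42 | 48 |
| One crenolanib dose counted as therapy | 7 + 42 to 10 + 42 | 49 to 52 |
| Event-start clock, onset day 28 | 28 + 42 | 70 |
| DLT period starting with crenolanib on day 7 to 10, onset on its last day (34 to 37) | 34 + 42 to 37 + 42 | 76 to 79 |
| Crenolanib counted, last dose assumed on day 35, 42 or 56 | each + 42 | 77, 84, 98 |

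Every result is later than day 30. The shortest gap is 43 − 30 = 13 days.

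**The two clocks disagree.** For an event starting on day *d* and a last dose on day *L*, the extended assessment ends on *d* + 42, but the criterion cannot be met before *L* + 42. Whenever *d* is earlier than *L*, assessment ends before the criterion can be met. An event starting on day 1 in Arm B is followed to day 43, but could qualify only from day 47.

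**Exposure at the fastest permitted accrual.** Six start on day 1. The sentence then permits six on day 31 and six on day 61.
- Before day 47: 6 further subjects in the arm.
- By day 70: 6 + 6 = 12 further subjects, or 12/24 = half of the planned arm.

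**Exposure at a slower, assumed rate of one start per 10 days per arm.** The first six start on days 1, 11, 21, 31, 41 and 51, and the limit never binds. If the sixth subject has the open event, that subject's day 47 is calendar day 51 + 46 = 97, and day 70 is calendar day 51 + 69 = 120.
- Starts after the sixth and before day 97: days 61, 71, 81 and 91, so 4.
- Starts by day 120: also days 101 and 111, so 6.

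The excess is then 4 to 6 rather than 6 to 12.

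**The case against.** The strongest reply is that the consequence depends on Section 12.2.1. A de-escalation section is where one would expect to learn whether a seventh subject waits for the first six. This stands, and it limits the point to the synopsis.

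A second reply is that the synopsis already implies a pause: six are enrolled and evaluated, and an expansion cohort follows. That reading is possible, but no hold is stated. The spacing sentence also fits it poorly. If enrolment stopped at six until evaluation was complete, a rolling limit of six would hardly ever bind. It mainly has work to do if a seventh subject may enter before the decision. At best the text is ambiguous.

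A third reply is that enrolment may be halted at any time after a safety review. That provision is discretionary and sits in the paragraph on monitoring after the dose has been determined.

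The scope is also narrow. Non-hematologic DLTs fall within the 28 days. A subject whose counts have recovered, or whose cytopenia is attributed to residual leukemia, leaves no open question. Delay has a price too: in the randomized trial of salvage therapies described in Section 2.1, overall survival was 3.5 and 3.3 months in the two arms. How long to hold enrolment is therefore partly a judgement.

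Four stronger readings are tempting, and the documents do not support them.
- *Days 47 and 70 as firm earliest and latest days.* They come from different clocks. Day 43 is possible on one, and days beyond 70 on either if the DLT period starts later or therapy includes later crenolanib.
- *12 to 18 of 24 subjects exposed too early.* That count includes the first six, who are treated under any design.
- *36 extra subjects across the trial (3 × 12).* This needs all three arms to start six on each of days 1, 31 and 61, which is 54 of 72 subjects by day 61. The text reviewed gives no accrual rate.
- *Marrow toxicity as the main risk of the combination.* No passage reviewed says so. The point needs only that the plan counts prolonged aplasia as a DLT.

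**Conclusion.** The mismatch holds on every reading of the synopsis: a slot is freed at 30 days, and no hematologic DLT can be established before day 43. Taken alone, and with six starts on day 1, the spacing sentence permits up to 6 further subjects per arm at the same dose before about day 47, and up to 12 by day 70. These are maxima that fall with slower accrual, and they matter only when a qualifying cytopenia is unresolved after the 28 days. The day-70 figure assumes that the DLT period starts with induction and that the event-start clock governs.

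A reader might infer that the protocol as a whole allows further cohorts at a dose not yet cleared. That cannot be concluded without Section 12.2.1. If that section contains a hold, what remains is a synopsis that does not reflect it.

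**What to change.** Reconcile the spacing sentence with the extended hematologic assessment and with Section 12.2.1. Replace the 30-day count with a limit tied to DLT evaluation, for example:

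- In each arm, at each dose under evaluation, no subject beyond the first six starts until the DLT evaluation of all six is closed.
- An evaluation is closed when the 28-day period is complete and any hematologic event that began in it has resolved, been attributed to residual leukemia, or completed its assessment.

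A limit on the number of open evaluations would not be enough. If five of six closed at day 28, five more could start while the sixth was still open.

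The amendment should also state which 6-week clock governs, when the DLT period starts, and whether therapy includes crenolanib. This review takes no view on which answer is right.

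**Cost.** A few sentences in an amendment, with no change to dose or sample size. When a cytopenia is unresolved after the 28 days, the arm waits about 6 weeks more (70 − 28 = 42 days), and longer if the last-dose clock governs and includes crenolanib. The other arms can keep enrolling. With staggered starts, the arm also waits out the sixth subject's 28 days even without a cytopenia. At the assumed one start per 10 days, that period ends on day 51 + 27 = 78, so the seventh subject starts on day 79 instead of day 61, 18 days later. If six start together, the 28-day wait is no longer than the present 30 days.
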